Associate Professor, Brown University

Address: Brown University, [name]

[contact]; [contact]; Email: [contact]

[name].

Role: MPI

Professor, Brown University

Assistant Director of Psychosocial Research, Butler Hospital

Address: Butler Hospital, [name]

[contact]; [contact]; Email: [contact]

[name].

Role: Study Statistician

Assistant Professor, Brown University

Address: Brown University, [name]

[contact]; [contact]; Email: [contact]

[name], Sc.M.

Role: Study Coordinator

Project Coordinator, Brown University

Address: Brown University, [name]

[contact]; [contact]; Email: [contact]

[name].

Role: Co-Investigator

C. S. Mott Endowed Professor of Public Health, Professor of OBGYN, Professor of Psychiatry and Behavioral Medicine, Michigan State University

Address: [name]

[contact]; [contact]; Email: [contact]

[name].

Role: Co-Investigator

Professor, Brown University

Address: Veterans Affairs Medical center, [name]

[contact] [name]; [contact]; Email: [contact]

[name].

Role: Co-Investigator

Director, Neuropsychology, Rhode Island Hospital and The Miriam Hospital

Address: [name]

[contact]; [contact]; Email: [contact]

PARTICIPATING STUDY SITES

Brown University: [name]
Contact: [name].

Butler Hospital: [name]
Contact: [name].

Lifespan: [name]
Contact: [name].

Michigan State University: [name]
Contact: [name].

Rhode Island Department of Corrections: [name]
Contact: [name]

PRÉCIS

Study Title

The Peace of Mind and Body Project: Treatment development of yoga for anger management in incarcerated adults

Objectives

Our proposed project will have two phases. Specific Aims for each phase include:

1. **Phase 1:** To refine our current manualized hatha yoga intervention and health education intervention to target high levels of anger dysregulation in prisoners.
 - a. To conduct focus groups with prisoners and criminal justice stakeholders (separately) to understand ways of increasing feasibility, acceptability, and efficacy of yoga for anger management as well as feasibility and acceptability of our control arm (health education);
 - b. To solicit feedback from experts in correctional mental health, addiction, and yoga; and
 - c. To modify our existing yoga treatment manual, health education manual, and instructor fidelity scales.
2. **Phase 2:** To conduct a pilot randomized clinical trial ($n = 40$) of hatha yoga vs. a health education group (attention control) for prisoners high in self-reported anger dysregulation. Participants will be enrolled in the active intervention for 10 weeks, and then be followed for 8 weeks.
 - a. To assess feasibility and acceptability of both the yoga class and the health education control group. We will assess credibility of the assigned intervention and expectancy for improvement for both groups at baseline, program satisfaction following program participation, participant adherence, ability to hold group classes (with a certain number of participants), and instructor fidelity to the manuals. We will conduct structured interviews following program participation to further understand and develop strategies to improve acceptability and feasibility.
 - b. To assess safety, we will track all adverse events in a structured fashion. We do not expect to see any serious adverse events definitely or probably related to study participation.
 - c. To assess feasibility of research procedures, we have benchmarks for recruitment rate, retention for study assessments, and reliability of instructor fidelity measures.

If successful, this project will provide us with materials, experience, and pilot data needed for the next step in this research, namely, a fully powered randomized clinical trial with anger dysregulation as the primary outcome.

Design and Outcomes

In Phase 1, we will conduct focus groups with prisoners and representatives from important criminal justice stakeholder groups (separately). We will also conduct individual interviews with prison administrators as key informants.

In Phase 2, we will conduct a pilot randomized clinical trial ($n = 40$) of hatha yoga vs. a health education group (attention control) for prisoners high in self-reported anger dysregulation. Participants will be enrolled in the active intervention for 10 weeks, and then be followed for 8 weeks. We will assess feasibility and acceptability of both the yoga class and the health education control arm, safety, and feasibility of research procedures.

In both programs, participants be involved in the study for approximately 15 hours over 18 weeks.

Interventions and Duration

Yoga classes. The manualized hatha yoga program will begin with an initial individual session with a yoga teacher to increase motivation for class attendance and self-efficacy for yoga practice between classes. Subsequently, participants will be asked to attend one 60-75 minute class per week for 10 weeks.

Health education. The program consists of information about general health topics. Participants will be asked to attend one 60-75 minute class per week for 10 weeks. Each week will cover a different topic.

Sample Size and Population

Phase 1 of the proposed project will include up to 18 prisoners and 6 representatives from important criminal justice stakeholder groups in focus groups. Also in Phase 1, we will conduct interviews with 3 separate prison administrators as key informants. Because RIDOC administrators may have a supervisory role over other RIDOC stakeholders, we believe it may not be prudent to have them participate in focus groups with other staff. Thus, prison administrators will be interviewed individually and separately as key informants (which are not considered to be human subjects, per the Brown University IRB).

Phase 2 of the proposed project will include 40 prisoners in the pilot. All prisoners will be high in self-reported anger dysregulation. Participants will be prisoners aged 18 to 70. We will recruit 20 men and 20 women to participate.

1. STUDY OBJECTIVES

1.1 Primary Objective

The primary aim of this treatment development research is to develop and establish the feasibility, acceptability, and safety of a hatha yoga intervention for prisoners with anger dysregulation and aggression. Development of the yoga intervention (and the health education control condition) will be informed by our prior experiences conducting research on yoga for depression, bipolar disorder, and chronic pain in community settings and by our prior experiences evaluating behavioral interventions for mental health outcomes in the criminal justice context.

The Specific Aims of this treatment development research are:

1. **Phase 1:** To refine our current manualized hatha yoga intervention and health education intervention to target high levels of anger dysregulation in prisoners.
 - a. To conduct focus groups with prisoners and criminal justice stakeholders (separately) to understand ways of increasing feasibility, acceptability, and efficacy of yoga for anger management as well as feasibility and acceptability of our control arm (health education);
 - b. To solicit feedback from experts in correctional mental health, addiction, and yoga; and
 - c. To modify our existing yoga treatment manual, health education manual, and instructor fidelity scales.
2. **Phase 2:** To conduct a pilot randomized clinical trial ($n = 40$) of hatha yoga vs. a health education group (attention control) for prisoners high in self-reported anger dysregulation. Participants will be enrolled in the active intervention for 10 weeks, and then be followed for 8 weeks.
 - a. To assess feasibility and acceptability of both the yoga class and the health education control group. We will assess credibility of the assigned intervention and expectancy for improvement for both groups at baseline, program satisfaction following program participation, participant adherence, ability to hold group classes (with a certain number of participants), and instructor fidelity to the manuals. We will conduct structured interviews following program participation to further understand and develop strategies to improve acceptability and feasibility.
 - b. To assess safety, we will track all adverse events in a structured fashion. We do not expect to see any serious adverse events definitely or probably related to study participation.
 - c. To assess feasibility of research procedures, we have benchmarks for recruitment rate, retention for study assessments, and reliability of instructor fidelity measures.

We hypothesize that we will hit all benchmarks in table 4 on page 38. If successful, this project will provide us with materials, experience, and pilot data needed for the next step

in this research, namely, a fully powered randomized clinical trial with anger dysregulation as the primary outcome.

2. BACKGROUND AND RATIONALE

2.1 Background on Condition, Disease, or Other Primary Study Focus

Prisoner mental health is an area of high public health significance. The United States (US) has the highest rates of incarceration and criminal justice (CJ) involvement in the world.¹ Nearly 7 million people pass through the US CJ system each year, and 1.6 million people are housed in US prisons at any given time.² In addition to the well documented and significant racial, ethnic, and socioeconomic disparities encountered in the CJ system,³ there is a disproportionately high mental health burden among those who are incarcerated. Indeed, the US CJ system has been described, by proxy, as the largest mental healthcare system in the United States.⁴ Roughly 50% of prisoners report a history of one or more psychiatric diagnoses,⁵ most commonly depressive and anxiety disorders, trauma-related disorders, psychotic-spectrum illnesses, and disorders of impulse control.⁶ Prisoners also report a disproportionately high rate of lifetime substance use disorders, ranging in prevalence from 25-58%,⁶⁻⁸ and as high as 74% among those with a history of psychiatric illness.⁵ Following from this substantial psychiatric and substance use morbidity, and further complicated by the high medical burden also documented in this population,⁹ prisoners are at significantly heightened risk for suicide and premature all-cause mortality, both in prison¹⁰ and upon community re-entry.¹¹

Of particular interest has been a focus on anger dysregulation. With significant transdiagnostic relevance, anger is a negative affective state of variable duration, ranging in intensity from “mild irritation or annoyance to intense fury and rage.”¹² In addition to being an affective experience, anger involves cognition and physiological arousal. Anger is typically associated with negative cognitions surrounding a triggering event, particularly those focused on themes of perceived injustice and attributions of blame.¹³ Anger is also typically marked by activation of the neuroendocrine system and autonomic arousal, consistent with a fight-or-flight response, with corresponding elevations in heart rate, muscle tension, skin flushing, and shortness of breath.¹⁴ Anger is frequently – though not always – paired with **aggression**, marked by behaviors that aim to “warn, intimidate, control, or attack, or gain retribution,”¹³ such as verbal or behavioral intimidation or punishment (i.e., in the form of interpersonal confrontation or violence) toward others.

Together, anger dysregulation and aggression are frequently encountered in the CJ setting, and in fact, may contribute to the very offenses that result in initial CJ involvement and incarceration.¹⁵ While incarcerated, anger dysregulation may contribute to affective distress and exacerbation of underlying mental health problems. Overt aggression further increases risk of disciplinary action,^{16,17} such as placement in restraints or prison seclusion,¹⁸ and may delay parole or release decisions.¹⁹ After prison release, anger dysregulation and aggression may precipitate clinical deterioration, and contribute to risk for reoffending and recidivism.^{20,21}

2.2 Study Rationale

In the criminal justice (CJ) system in the US, there are high rates of mental health and substance use disorders. Although prisons must provide treatment, the CJ system is resource-poor and the presenting problems of prisoners are diverse. To maximize efficiency in the CJ context, recent efforts focus adjunctive interventions on symptoms that are most detrimental to prisoners, and that are shared across diverse conditions. Of particular interest has been anger dysregulation, as this is prevalent in CJ-involved populations, contributing not only to distress and exacerbation of other mental health problems, but also to risk of aggression. Overt aggression further increases risk for prison behavioral infractions or placement in restraints or seclusion, and may delay parole or release decisions.

There are many limitations to existing approaches to anger management in prison. We propose that hatha yoga could serve as a useful adjunctive treatment for anger within prisons. In addition to preliminary research showing that yoga programs may improve anger regulation, research has also demonstrated benefits of yoga for related symptoms of depression, anxiety, and trauma-related emotion reactivity and arousal. Yoga may be delivered in a relatively low-cost fashion. Finally, prisoners may view yoga as less stigmatizing than more traditional anger management interventions, particularly given its focus on physical body awareness/movement and on overall wellness.

Despite a recent proliferation of yoga programs for various problems in prisons, empirical research on this topic is minimal, with a small number of studies limited by significant methodological concerns. We propose to conduct *systematic* treatment development research that would prepare us to study whether yoga (vs. a health education control group) is an effective adjunctive treatment for prisoners with anger dysregulation.

3. STUDY DESIGN

In Phase 1, we will conduct 4 focus groups, composed of approximately 6 individuals each (N=24). To achieve this number, we will consent up to 72 individuals to achieve our enrollment goals. The first 3 focus groups will be comprised of 18 prisoners in each of the 3 RIDOC facilities where we plan to conduct the next phase of this research project (men's minimum, n=6; men's medium, n=6; women's combined minimum/medium n=6). The fourth focus group will consist of 6 representatives from important criminal justice stakeholder groups, including correctional officers, prison treatment staff, and justice-focused members of the public. To complement the focus groups, we will conduct separate interviews (n=3) of prison administrators as key informants. Enrollment period for this phase will last approximately 4 months.

In Phase 2, we will consent up to 175 prisoners in order to achieve our enrollment goal of 40 prisoners who meet study inclusion for randomization to conditions in the pilot RCT. Participants will be recruited from the Rhode Island Department of Corrections (RIDOC) in Cranston, RI. They will be randomized to either the yoga intervention or the health education group. The study research assistant will randomize participants in the prison using small opaque envelopes labeled with a number and the strata (for example, male medium 1, male medium 2, etc.). Depending on group assignment, participants will be invited to participate in 10 weekly sessions of yoga or the health education group, to be held in the facility where they reside. Group classes will be held in relevant spaces in the facilities at RIDOC (i.e. classrooms, chapels, library, etc.). The hatha yoga intervention will involve an initial individual session with a yoga teacher, designed to increase motivation for yoga class attendance and self-efficacy for adapted yoga practice between classes. Following the initial individual session, participants will be invited to attend one 60-75 minute yoga class for 10 weeks in the prison facility where they reside. Registered yoga teachers will deliver the intervention. The Health education control group will be a 10-week program that consists of weekly 60-75 minute group classes in the prison facility where the participants reside. In classes, instructors will provide information about general health topics through a variety of means such as slides, handouts, and/or audio and video clips. This class will be taught by instructors with experience working in correctional settings and post-baccalaureate experiences or certification in a relevant health care field. In addition to the baseline assessment, outcome assessments will occur at 5 weeks (mid-intervention), 10 weeks (post-intervention), 14 weeks (qualitative interview for yoga participants only), and at 8 week follow-up, for a total length of participation of each individual participant of 4.5 months. Enrollment period for this phase will last approximately 7 months.

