5. STUDY INTERVENTIONS

5.1 Interventions, Administration, and Duration

Hatha yoga intervention. The yoga intervention will involve an initial individual session with a yoga teacher, designed to increase motivation for yoga class attendance and self-efficacy for adapted yoga practice (see below) between classes. Following the initial individual session, participants will be invited to attend one 60-75 minute yoga class for 10 weeks in the prison facility where they reside. Class length must be flexible as research staff do not control exactly when all participants will be able to arrive at the designated classroom. Registered yoga teachers will deliver the intervention. Potential risks include loss of privacy or breach of confidentiality, and mild physical injury.

Health education control group. To match for attention, the control condition will be a 10-week program that consists of weekly 60-75 minute group classes in the prison facility where the participants reside. In classes, instructors will provide information about general health topics through a variety of means such as slides, handouts, and/or audio and video clips. This class will be taught by instructors with experience working in correctional settings and post-baccalaureate experiences or certification in a relevant health care field. Potential risks include loss of privacy or breach of confidentiality.

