6.4. Material Inducements

In phase 1 (focus groups), we will compensate participants \$20 for completion of the focus groups. For prisoner participants, this compensation will be in the form of money paid directly into their commissary account at the RIDOC. For stakeholder participants, this compensation will be in the form of a money order or gift card, paid to them directly upon completion of the focus group.

In phase 2 (pilot RCT), we will compensate participants \$20 for each of the follow-up assessments (mid-intervention, post-intervention, 4 week follow-up (yoga participants only) and 8 week follow-up). In total, participants may receive up to \$80 compensation. Similar to our procedures for prisoner participant compensation in phase 1, the compensation will be in the form of money paid directly into their commissary account at the RIDOC. If a participant is released from the RIDOC while still enrolled in the study, and completes any follow-up assessment in the community, this compensation will be provided in the form of a money order or gift card. Additionally, a participant may also choose to have us mail their compensation to a family member or significant other of their choosing.

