Feasibility and Acceptability—Research Procedures	
Recruitment rate	Average of 6 enrolled per month
Retention rate	80% complete week 10 assessment; 70% complete wk. 18 assessment
Completion of items on assessment instruments	At least 90% of items are completed on each assessment instrument (so each will be valid).

9.5.2 Secondary/ Exploratory Outcomes.

In Phase 2, we will also examine change in key variables over time. This is an exploratory analysis.

Specifically, we will look at change over time the in the following variables. The primary outcome in a subsequent efficacy study is in **bold and underlined**. Secondary outcomes are in standard text. *Potential mechanisms are in italics*.

- **NAS-Provocation Inventory from BL to wk10**; BL to wk18.
- Aggression Questionnaire – Short Form, BL to wk10; BL to wk18.
- Number of behavioral infractions in Prison, BL to wk10; BL to wk18
- PHQ-9, BL to wk10; BL to wk18
- PROMIS Anxiety, BL to wk10; BL to wk18
- SF-12 physical health composite score, BL to wk10; BL to wk18
- SF-12 mental health composite score, BL to wk10; BL to wk18
- *Anger rumination scale, BL to wk10; BL to wk18*
- *Experiences Questionnaire, BL to wk10; BL to wk18*

- *Stroop Color and Word Test, BL to wk10; BL to wk18*

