9.6 Data Analyses

Qualitative Data Analysis. We will identify themes through team-level review of transcripts and group discussions.

Quantitative Data Analysis. In the past, researchers have used pilot data to estimate an effect size for future power calculations. Kraemer et al.⁶⁰ emphasized the limitations of this practice due to the likelihood of large standard errors surrounding effect size estimates, and the concern that ultimately, large-scale RCTs should be powered to detect between-group differences considered to be *minimally clinically significant*.

Using data from the pilot RCT, we will examine differences in means and SDs (or frequencies) of key variables (e.g., NAS total score, NAS subscale scores, secondary outcomes, and possible mechanisms) across time points using repeated-measures ANOVA. We will use effect size estimates to characterize differences between groups at each timepoint and will calculate associated 95% confidence intervals of these estimates in order to understand the precision, or lack thereof, of our estimates. We recognize that, due to the likely size of these CIs, these analyses may not permit definitive conclusions.

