Confidentiality and loss of privacy. The greatest potential risks to those participating in the research are legal or social, caused by the inadvertent loss of confidential information obtained during the data collection process. That is, a participant's identity may be inadvertently exposed or questionnaire material may be released or disclosed to unauthorized persons. In the case of such a breach, serious personal and social consequences could conceivably occur. However, such risks can be minimized by instituting the proper procedures to protect confidentiality and by having resources in place to provide counseling and referrals. We have extensive experience taking appropriate measures to safeguard confidential information in research with criminal justice populations. We will minimize potential risks due to loss of confidentiality of research data by having all information collected and handled by research staff, including study interventionists, trained to deal appropriately with sensitive clinical issues. All participants will be informed about the limits of confidentiality concerning suicidal intent, homicidal intent, suspected child abuse, suspected elder abuse, and other prison-required mandatory reporting issues (i.e., sexual contact within the prison, weapons in the prison, prison escape plans). All information will be treated as confidential material and will be available only to research staff. All information will be kept in locked file cabinets at Brown University. Computer data files will be kept on Brown's secure research servers, will be available only to authorized personnel, and no names or obvious identifying information will be stored in data files. No participant will be identified in any report of the project. Written consent will be obtained to contact other persons for the purpose of locating the participant for follow-up and participants can refuse or revoke such requests. Participants will update their contact information and contact person (in the unanticipated event of a reduced sentence and release prior to study completion) at each assessment point to ensure that this information remains appropriate. To further protect participants, there will be a **Federal Certificate of Confidentiality** for this project, which is now automatically awarded by NIH when a proposal is funded. Potential subjects will be informed that a Certificate of Confidentiality has been obtained for this project and that this certificate will protect the investigators from being forced to release any research data in which participants can be identified, even under court order or subpoena, although this protection is not absolute. Potential participants will be informed of the situations during the informed consent process (and as documented in the informed consent document) in which they may not be protected under the Certificate of Confidentiality. No information about participants will be released without their permission or where required by law.

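### After week 10, scheduled contact and payment differ by arm: only yoga participants have a paid week-14 interview before the week-18 assessment

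*Combined protocol and SAP*

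**What the plan says.** Protocol section 3 places a yoga-only qualitative interview between the week-10 and week-18 assessments: "14 weeks (qualitative interview for yoga participants only), and at 8 week follow-up". Table 3 and sections 6.2.6 and 7.1 repeat it. Section 9.1.2 describes a yoga-only interview on intersectional stigma and resiliency, which matches it. The revision history shows that the interview came in with version 1.6.

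Section 6.4 pays $20 for each follow-up, including the "4 week follow-up (yoga participants only) and 8 week follow-up". It gives one ceiling for everyone: "In total, participants may receive up to" $80. No separate figure is given for health education.

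The target outcomes table in section 9.5.1 sets the retention benchmark without reference to arm: "80% complete week 10 assessment; 70% complete wk. 18 assessment". The same section says that missed targets lead to investigation and discussion, and could lead to a decision not to propose the large trial.

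Section 9.6 plans comparisons between arms: "We will use effect size estimates to characterize differences between groups at each timepoint". That includes week 18.

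Nothing in the protocol or the Data Safety Monitoring Plan (DSMP) mentions the unequal contact or plans to report retention by arm.

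**The concern.** The week-14 interview is a post-randomisation difference between arms that is not part of the yoga programme. It consists of a further one-to-one contact with research staff and a further payment, four weeks before the final assessment. Either could make a yoga participant more likely to complete week 18. A personal interview on stigma and resilience could also colour self-reports given four weeks later. Health education participants have no scheduled contact between weeks 10 and 18.

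Two outputs are exposed. The pooled week-18 retention figure could meet its target partly because of a contact that only one arm received, and a pooled figure would not show this. The week-18 effect sizes could also reflect the interview, or differential retention, as well as the intervention. Both are meant to inform the next trial, whose follow-up schedule may not include such an interview.

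**Working it through.** **1. The plan's own payment figure.** Section 6.4 and Table 3 give $20 per paid follow-up.

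- Yoga: weeks 5, 10, 14 and 18, so 4 × $20 = $80. This reproduces the stated ceiling.
- Health education: weeks 5, 10 and 18, so 3 × $20 = $60. The stated ceiling cannot be reached in this arm.

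**2. Scheduled contacts after week 10 (Table 3).**

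| | Yoga | Health education |
|---|---|---|
| Contacts | Weeks 14 and 18 (2) | Week 18 (1) |
| Longest scheduled gap | 4 weeks | 8 weeks |

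**3. Timing against custody.** Inclusion criterion 3 in section 4.3 asks for at least 90 days of expected remaining custody, and 90/7 = 12.9 weeks. Week 14 is day 98 and week 18 is day 126. An eligible participant can therefore be released before either visit, although protocol section 7.1 and DSMP section 5 call release during participation unlikely.

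**4. Is there an extra update of contact details at week 14?** DSMP section 5 says "Participants will update their contact information and contact person" at each assessment point. Protocol sections 3, 6.2.6 and 7.1 list week 14 among the assessments. But the paragraphs on distress in protocol section 7.1 and DSMP section 5 count four formal assessments: baseline and weeks 5, 10 and 18. The documents conflict, so a week-14 update is possible but not established.

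**5. Sensitivity of the retention benchmark.** The target is 0.70 × 40 = 28 retained. DSMP section 7.2 gives 1:1 allocation, so about 20 per arm. Let retained counts be independent: Y ~ Bin(20, p + d) in yoga and H ~ Bin(20, p) in health education. The quantity is P(Y + H ≥ 28). The documents give neither p nor d, so both are assumptions shown over a range.

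| Base retention p | d = 0 | d = 5 points | d = 10 | d = 15 | d = 20 |
|---|---|---|---|---|---|
| 60% | 0.13 | 0.21 | 0.31 | 0.44 | 0.58 |
| 65% | 0.31 | 0.44 | 0.58 | 0.71 | 0.83 |
| 70% | 0.58 | 0.71 | 0.82 | 0.91 | 0.96 |

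Check: with p = 0.70 and d = 0, the single binomial tail for 28 or more of 40 is 0.577, which agrees.

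A pooled pass can hide a weak arm. For example, 16/20 in yoga and 12/20 in health education give 28/40 = 70%, with health education at 60%.

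**6. Could the trial detect such a difference?** With 20 per arm and 70% in both, the 95% half-width for the difference in retention is 1.96 × √(2 × 0.70 × 0.30/20) = 0.28, or 28 points. Power to detect a gap of 10, 15 or 20 points above 70% is 11%, 20% and 35%. For the week-18 standardised effect, if 14 per arm remain (70% of 20), the half-width near zero is about 1.96 × √(2/14) = 0.74.

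**The case against.** The strongest reply is that this is a small purposive interview in an unpowered pilot. The clinical target is the Novaco Anger Scale at week 10 (Table 5), before the contact. Week-18 change is exploratory, and Table 5 specifies Cohen's d only to week 10. Section 9.6 itself warns that the estimates may be too imprecise for firm conclusions. No between-arm test of retention is planned. Paying those who give up time for an interview is consistent with the DSMP commitment to payment in proportion to time. All of this stands, and it limits the point to week 18.

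A reader might infer more than the documents support:

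- **That the attention match is broken.** It is claimed for the class programme: "To match for attention, the control condition will be a 10-week program". Week 14 lies outside it. Contact was also not identical before, since yoga begins with an individual teacher session for which no health education counterpart is described.
- **That yoga certainly gets an extra locator update.** As step 4 shows, this is an inference from conflicting lists.
- **That the interview rehearses the benefits of yoga.** Its stated subject is stigma and resiliency during incarceration. Programme feedback is collected at week 10, with no arm restriction in Table 3.
- **That health education participants will be lost after day 90.** Ninety days is a minimum, and sections 4.4.3 and 6.2.6 plan locator permissions and community follow-up for both arms.

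The objection does not remove the plain imbalance before week 18, or the absence of any by-arm retention figure with which to examine it.

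**Conclusion.** The point holds in limited form. After week 10, scheduled contact (2 against 1) and maximum payment over the trial ($80 against $60) are unequal by arm. This could affect the pooled week-18 retention benchmark and the exploratory week-18 between-group effect sizes. The week-10 clinical target is not touched.

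That the imbalance exists follows directly from the schedule. That it changes retention or self-reports is plausible but not shown, and the probabilities above rest on assumed rates. With a half-width of about 28 points, an observed retention gap could not be attributed to the interview either. The case for change is that the difference is avoidable and cheap to remove, not that a bias of known size is present.

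**What to change.** 1. For yoga participants who have not yet reached week 14, hold the stigma and resiliency interview after their week-18 forms are complete. Amend Table 3 and sections 3, 6.2.6, 6.4 and 7.1 to match. The cost is a small schedule amendment, about four weeks' delay and perhaps a few missed interviews. If the interview shares the week-18 visit, that visit would carry $20 + $20 = $40 in yoga against $20 in health education. A separate appointment afterwards avoids tying the extra payment to the week-18 visit.
2. Report week-18 retention by arm beside the pooled figure in section 9.5.1. This costs almost nothing.
3. In section 6.4, state the maximum compensation for each arm.
4. Reconcile whether week 14 is an assessment point and whether contact details are updated then (protocol sections 3, 6.2.6 and 7.1; DSMP section 5).
5. For yoga participants already interviewed at week 14, give their number and list the unequal contact as a limitation of week-18 comparisons. The documents do not show how many there are, and moving the interview now may leave yoga participants on two schedules, which should be stated.

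A matched week-14 contact for health education is an alternative, at no more than 20 × $20 = $400 in payments. It is more debatable, because paying $20 for a brief contact sits uneasily with the commitment to pay in proportion to time.
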